### **Cost-effectiveness**

For the CUA and CEA, missing cost and effect data will be imputed using multivariate imputation by chained equations. The results of the imputed datasets will be pooled using Rubin's rules. LMM, with the same three-level structure as described above, will be performed to estimate cost and effect differences. See the tables below. In order to account for the highly skewed nature of cost data, bias-corrected and accelerated bootstrapping with 5000 replications will be used to estimate 95% confidence intervals around the cost differences. Incremental Cost-Effectiveness Ratios (ICERs) will subsequently be calculated by dividing the differences in costs between trial arms by the difference in QALYs for the CUA and the differences in combined measure of pain and disability for the CEA. The uncertainty surrounding the ICERs will be graphically illustrated by plotting bootstrapped incremental cost-effect pairs on cost-effectiveness planes. Moreover, cost-effectiveness acceptability curves (CEACs) will be constructed to provide a summary measure of the joint uncertainty of costs and effects. CEACs indicate the probability of the Stratified Blended Approach being cost-effective in comparison to usual physiotherapy care at different willingness-to-pay values. To test the robustness of the trial results, several sensitivity analyses will be performed.

**Tabel 3. Mean costs per participant in the Stratified Blended Approach arm and usual physiotherapy (PT) arm and mean differences between both arms during 9 months follow-up**

	SBA (N = ); mean costs in € (SEM)	Usual PT (N = ); mean costs in € (SEM)	Unadjusted mean cost difference in € (95% CI)	Adjusted mean cost difference in € (95% CI)
Intervention a				
Primary healthcare				
Secondary healthcare				
Medication a				
Sport				
Informal care				
Absenteeism				
Presenteeism				
Unpaid productivity				
Healthcare costs b				
Total costs				

aSignificant difference between Stratified Blended Approach and usual PT; bHealthcare costs = intervention costs + primary healthcare costs + secondary healthcare costs + medication costs adjusted for sex, age, BMI, level of education, type of complaints (neck or shoulder), physical functioning at baseline, pain at baseline and utility score at baseline

**Table 4. Differences in pooled mean costs and effects**

Analysis	N SBA	N Usual	Outcome	ΔC	ΔE	ICER Euro/point	Distribution CE-plane (%)
				(95% CI) In €	(95% CI) In points		
Main analysis 1:			QALYs (0–1)				NE a SE b SW c NW d
Total costs and imputed dataset			region-specific pain and disability score (0–100)				
Main analysis 2:			QALYs (0–1)				
Healthcare costs and imputed dataset			region-specific pain and disability score (0–100)				
Sensitivity analysis 1:			QALYs (0–1)				
Complete cases			region-specific pain and disability				

	score (0–100)
Sensitivity analysis 2:	QALYs (0–1)
Per-protocol and imputed dataset	region-specific pain and disability score (0–100)

CI confidence interval, C costs, CE-plane cost-effectiveness plane, E effects, ICER incremental cost-effectiveness Ratio costs are expressed in 2015 Euros; aThe northeast quadrant of the CE plane, indicating that SBA is more effective and more costly than usual PT; bThe southeast quadrant of the CE plane, indicating that e-Exercise is more effective and less costly than usual physiotherapy; cThe northwest quadrant of the CE plane, indicating that SBA is less effective and more costly than usual PT; dThe southwest quadrant of the CE plane, indicating that SBA is less effective and less costly than usual PT

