## Statistical Principles

### Confidence intervals and *P* values

All analyses are described in this statistical analysis plan and are therefore considered *a priori* analyses. If applicable, *post hoc* analyses will be identified as such in the articles.

For all analyses, a two-tailed significance level of  $p < 0.05$  is considered to be statistically significant. All confidence intervals presented will be 95% and two-sided. The assumption of normality will be checked with Q-Q-plots and histograms. The interquartile range will be reported for skewed data.

Statistical analysis will be performed using IBM SPSS 27 or statistical package STATA. During the analyses, the researchers will be blinded to group allocation until the entire analysis will be completed.

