### Adherence/compliance and Protocol deviations

Compliance to the smartphone app with e-Exercise modules in the Stratified Blended Approach arm will be assessed by quantitative data on the usage. These data will automatically be stored on the backend of the app. Additionally, all patients will be asked in the first follow-up questionnaire whether they received and used an app or paper-based workbook as part of their physiotherapy treatment. Participants will be considered compliant to the e-Exercise modules (app) if they log in once a week in 67% (low risk: 2 weeks over 3 weeks) or 75% (medium/high risk: 9 weeks over 12 weeks) of the total amount of weeks. Participants will be considered to comply to the paper-based workbook if they self-report that they used the workbook at T1 (3 months). Descriptive statistics on the percentage adherent (plus N, mean, SD, median, minimum, maximum) will be summarized per arm.

Because of the pragmatic design of the trial, there are no protocol deviations that might impact the analyses. An overview of the content of physiotherapy sessions & number of physiotherapy sessions will be described for both arms.

[figure not shown]

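### Do the mislabelled footnotes, preset significance marks and 2015 price year in the economic table shells (SAP Tables 3 and 4) call for a change to the plan?

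*SAP*

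**What the plan says.** The Cost-effectiveness part of Analysis methods ends with two blank tables.

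- **Table 4, quadrant letters.** The column heads list NE, SE, SW and NW with letters a, b, c and d in that order. Footnote c reads "The northwest quadrant of the CE plane, indicating that SBA is less effective and more costly than usual PT" and footnote d reads "The southwest quadrant of the CE plane, indicating that SBA is less effective and less costly than usual PT".
- **Table 4, name of the intervention.** Footnotes a, c and d compare SBA with usual physiotherapy. Footnote b has "indicating that e-Exercise is more effective and less costly than usual physiotherapy". In the section on adherence, e-Exercise denotes the app modules within the arm: "Compliance to the smartphone app with e-Exercise modules in the Stratified Blended Approach arm".
- **Table 3, significance mark.** Letter a is defined as "Significant difference between Stratified Blended Approach and usual PT". It already stands on the intervention row ("Intervention a") and on the medication row, with all result cells empty.
- **Table 4, price year.** The legend says that "costs are expressed in 2015 Euros". Timing of final analysis anticipates the lock in December 2023.

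**The concern.** Taken together, these points suggest a results template carried over from elsewhere without proofreading. A reader who followed the letters alone would take the southwest share as the dominated outcome (worse and dearer) and the northwest share as the trade-off (worse but cheaper). Footnote b attributes the most favourable quadrant to one component of the intervention, although some patients in the arm use a paper workbook instead. A significance mark placed before any data exist could survive into print and claim a difference that was not found. A price level 8 years old would make every cost difference and ratio look smaller than in current money. The SAP also does not say how its various unit prices are brought to that year.

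**Working it through.** **1. Letters against footnotes (Table 4).**

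| Letter | Column head | Footnote text | Match |
|---|---|---|---|
| a | NE | northeast: more effective, more costly | yes |
| b | SE | southeast: more effective, less costly | yes |
| c | SW | northwest: less effective, more costly | no |
| d | NW | southwest: less effective, less costly | no |

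Two of four letters are crossed. Within every footnote, the quadrant name agrees with its description. The shares are counted from bootstrapped cost-effect pairs by their position on the plane, so a footnote letter does not enter the calculation. The printed words southwest and northwest also contradict the crossed letters on sight.

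**2. Name.** Three of four footnotes say SBA, and the table's sample-size columns are for SBA and usual care. The comparison in footnote b cannot be anything else.

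**3. Preset marks (Table 3).** Two of 11 rows are marked. The rule that decides significance is set under Confidence intervals and P values ("For all analyses, a two-tailed significance level of" p < 0.05), and Table 3 has 95% confidence interval columns for the same rows. If a preset mark were published unedited, it would be wrong with probability 1 − 0.05 = 0.95 when there is no true difference, and 1 − 0.80 = 0.20 if power were 80% (assumed; the SAP gives no power for medication cost). Those figures restate alpha and power. They apply only if nobody edits the shell when filling it. The interval beside the mark would show the disagreement.

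**4. Price year.** The span to the lock year is 2023 − 2015 = 8 years. The SAP gives no inflation rate, so 1% to 4% per year is assumed:

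- Factor: 1.01^8 = 1.083; 1.04^8 = 1.369.
- Cost difference of 200 Euro (assumed): 200 × 1.083 = 216.6; 200 × 1.369 = 273.8.
- Ratio with an effect of 5 points (assumed): 200/5 = 40 Euro per point, becoming 43.3 to 54.8.

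For the plane and curve, take independent normal differences: cost mean 200, SD 300; effect mean 5, SD 2.5 (all assumed).

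- Quadrant shares: P(effect > 0) = Φ(5/2.5) = 0.977 and P(cost > 0) = Φ(200/300) = 0.748. This gives NE 73.1%, SE 24.7%, SW 0.6%, NW 1.7%. Multiplying all costs by one positive factor changes no sign, so these shares stay the same.
- Curve at willingness to pay L = 100: Φ((5 × 100 − 200)/√((2.5 × 100)² + 300²)) = Φ(300/390.5) = 0.779.
- Costs and L both scaled by the factor: it cancels, and the result is again 0.779.
- Costs scaled but L kept at 100: Φ(283.4/409.9) = 0.755 at factor 1.083, and Φ(226.2/480.8) = 0.681 at factor 1.369.

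The last line is the only movement. It compares costs in new prices with a threshold in old ones. The SAP fixes no threshold; it plans the curve over a range of values.

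**The case for a change.** The strongest case for acting is that the label slips are plain errors, cost almost nothing to correct and sit in tables meant to be filled in and published. If the intervention proved less effective, the two west quadrants would carry most of the result, and confusing a dominated outcome with a trade-off would then matter. On prices, the SAP draws on standard costs, prices from professional bodies, micro-costed intervention costs, a shadow price for unpaid work and gender-specific price weights. The 2015 label is true of every row only if all of these are converted to that year, and the method of conversion is not given.

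The errors of labelling stand as described. They are proofreading points in blank shells, and anyone entering results would meet the conflict between letter and quadrant name, or between mark and interval. The price point stands only as missing detail. The legend does name one common year, and that year is compatible with the costing manual dated 2016 in the reference list. Any base year is legitimate if costs are converted to it, and indexing unit prices is routine work for a health economist. A later base year would be a preference.

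The sign of the effect in the cost-effectiveness ratio might also be questioned, since a higher pain and disability score is worse. The footnotes already define the quadrants by more or less effective, so the orientation of the plane is settled and only the printed sign is left open.

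**Conclusion.** No change to the plan follows. Two crossed letters, one wrong name and two preset marks are clerical slips in unfilled secondary tables. They alter no estimand, model, population, error rate or computed quadrant share, and the primary effectiveness analysis is untouched. The marks are not evidence of an early look at results: the cells are empty, and the SAP keeps the researchers blinded to allocation until the analysis is complete. The 2015 price year is internally consistent. Under the assumed inflation range it would rescale reported costs by a factor of 1.08 to 1.37, with quadrant shares unchanged and the acceptability curve unchanged when the threshold is in the same prices. That rests on one common factor for all prices and on 2023 as the comparison year. An earlier comparison year would give a smaller factor at the same inflation rates. The unstated conversion method is a gap that the analysts can be expected to fill sensibly.

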## Supplementary Table

Table 5. Characteristics per subgroup at T0

Variable	T0 value				
	Low Risk		Medium Risk		High Risk
	App	Paper-based	App	Paper-based	App
No. of respondents					
Age, years					
Sex, female (%)					
Education level					
Low					
Middle					
High					
Type of complaints (%)					
Predominantly Neck					
Predominantly Shoulder					
Duration of physical symptoms					
<3 weeks					
3 – 12 weeks					
>12 weeks					
BMI, kg/m2					
Risk of persistent disabling pain (using the STarT MSK Tool)* (%)					
Low					
Medium					
High					
Smartphone or tablet access, yes (%)					
Smartphone or tablet usage					
None					
1 – 3 apps per week					
4 – 10 apps per week					
>10 apps per week					
No. of comorbidities					
0					
1					
≥2					
Combined region-specific pain and disability score†					
Health-related quality of life‡					
MVPA (average minutes per day)§					
Pain intensity¶					
Illness perceptions#					
Self-management skills**
